5.5.2.1 Deaths, Other Serious Adverse Events, and Other Significant Adverse Events

A listing of deaths will be produced.

The number (percentage) of subjects with treatment-emergent serious adverse events (SAEs) will be listed and summarized by MedDRA PT and decreasing frequency.

The number (percentage) of subjects with TEAEs leading to discontinuation from study drug will be listed and summarized by MedDRA PT and decreasing frequency

Standardized MedDRA Query (SMQ) will be used to identify relevant terms for the following TEAEs. All of these TEAEs will be summarized by narrow terms.

- TEAEs suggestive of abuse potential: SMQ of drug abuse, dependence and withdrawal
- TEAEs related to alertness and cognition: SMQ of dementia
- TEAEs related to hostility/aggression: SMQ of hostility/aggression
- TEAEs related to psychosis and psychotic disorder: SMQ of psychosis and psychotic disorders
- TEAEs related to status epilepticus/convulsions: SMQ of convulsions
- TEAEs related to drug related hepatic disorder abnormalities: SMQ of drug-related hepatic disorders
- Cardiac and electrocardiogram (ECG) TEAEs: SMQs of cardiac arrhythmia terms (including bradyarrhythmias and tachyarrhythmias, arrhythmia related investigations, signs and symptoms, cardiac failure, cardiomyopathy, ischaemic heart diseases, and Torsade de pointes/QT prolongation
- Rash: SMQ of severe cutaneous adverse reactions and hypersensitivity

5.5.3 Laboratory Values

Laboratory results will be listed.

5.5.4 Vital Signs

Vital signs data will be listed.

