The AE verbatim descriptions (investigator terms from the CRF) will be classified into standardized medical terminology using MedDRA. Adverse events will be coded to the MedDRA (Version 15 or higher) lower level term closest to the verbatim term. The linked MedDRA PT and primary SOC are also captured in the database.

Laboratory Values

Clinical laboratory values will be evaluated for each laboratory parameter by subject. Descriptive summary statistics (eg, mean, SD, median, minimum, maximum) for the laboratory parameters and changes from Baseline to the last on-treatment visit will be summarized.

Laboratory test results will be assigned a LNH classification according to whether the value was below (L), within (N), or above (H) the laboratory parameter's reference range. Shift tables will be used to compare the baseline LNH classification to the LNH classification at end of study.

Clinical laboratory results post-baseline will be evaluated for markedly abnormal values. [Appendix 1](#) presents the modified National Cancer Institute-common toxicity criteria (NCI-CTC) criteria that will be used to identify subjects with markedly abnormal laboratory values. For the incidence of markedly abnormal laboratory values, each subject may be counted once in the laboratory parameter value high and in the laboratory parameter low categories as applicable.

Vital Signs

Vital sign values will be evaluated on an individual basis by subject. Abnormal vital sign values will be identified as those outside (above or below) the reference range, where appropriate. Descriptive summary statistics (eg, mean, SD, median, minimum, maximum) for vital sign parameters and changes from baseline and to the last on-treatment visit will be evaluated.

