8.2.2 Treatment Duration for Safety Analyses

The treatment duration for non-AE safety variables is considered to begin at or after the first dose of study drug on Day 1 and ends 14 days after the last dose of double-blind study medication. For AEs, the treatment duration is considered to begin on Day 1 and ends 28 days after the last dose of double-blind study medication.

The post-treatment duration is considered to begin on the day after the treatment duration for safety. Since it is not always possible for all study participants to come in for their clinic visits on the exact day specified in the protocol schedule, the visit week of a subject's visit will be based on the actual visit occurring during the treatment duration. These visits will be used to create by visit summaries for laboratory, and vital signs data. The end of treatment value is the last non-missing value in the treatment duration.

Any concomitant medication taken within the 14 days after the last dose data will be listed/summarized as part of the concomitant medication listing/table.

AEs for the subject were collected and reported on CRF starting from the time the subject signed informed consent to the last visit in the Treatment Phase following the subject's last dose. Serious AEs were collected for 28 days after the last dose.

For summaries of safety by time points, the time points will be relative to date of first dose. For standardized reporting, study day windows relative to the first dose (Day 1) in the study will be applied to determine into which week the data will be mapped. Scheduled, unscheduled, and early withdrawal visits will be mapped to weeks. [Table 2](#) below gives the mapping of relative day ranges to week for vital sign assessments. [Table 3](#) below gives the mapping of relative day ranges to week for laboratory assessments. If a subject did not have a recorded observation falling within a given range of days in order to be assigned to a week, the subject's data for that week will be regarded as missing for summarization purposes. If there are two or more assessments in the same window then:

- if the window is the baseline assessment, then the latest assessment will be used in the summary tables;
- if the window is the follow-up assessment, then the latest assessment will be used in the summary tables;

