5 STATISTICAL METHODS

All descriptive statistics for continuous variables will be reported using mean, standard deviation (SD), median, minimum and maximum. Categorical variables will be summarized as number (percentage) of subjects.

In general, the scope of endpoints and analyses will include the entirety of perampanel exposure (Core and Extension A).

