5.1.2 Secondary Endpoints

The following key secondary endpoints will be evaluated sequentially using the FAS:

1. Median percent change in total seizure frequency per 28 days during double –blind treatment (Titration Period and Maintenance Period) relative to the Prerandomization Phase.
2. The 50% responder rate in the Maintenance Period of the double-blind treatment relative to the Prerandomization Phase for drop seizures
3. The 50% responder rate in the Maintenance Period of the double-blind treatment relative to the Prerandomization Phase for total seizures.

Other secondary endpoints are:

4. Median percent change in non-drop seizure frequency per 28 days during double-blind treatment (Titration Period and Maintenance Period) relative to the Prerandomization Phase

5. Proportion of subjects with 75%, and 100% responder rates for drop, non -drop, and total seizures in the Maintenance Period relative to the Prerandomization Phase
6. Proportion of subjects with 50% responder rate in the Maintenance Period of the doubleblind treatment relative to the Prerandomization Phase for non-drop seizures
7. Physicians' global evaluation of the subject's overall changes in symptoms (using a 7-point Likert scale with 1=very much improved and 7=very much worse) at the end of the double-blind treatment
8. Incidence of AEs and SAEs, changes in clinical laboratory values, and vital signs
9. Model-derived average perampanel concentrations at steady state ($C_{av,ss}$) during the Maintenance Period of the Core Study

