5.5 SAFETY ANALYSES

All safety analyses will be performed on the Safety Analysis Set (Extension). Treatment-emergent adverse events will be summarized. The incidence of on treatment suicidality as measured by the C-SSRS will be summarized. Clinical laboratory parameters and vital signs data will be listed. Study Day 1 for all safety analyses is defined as the date of the first dose of perampanel.

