8.2 SAFETY DATA HANDLING

8.2.1 Baseline safety

The baseline value for all safety endpoints will be the last non-missing measurement occurring prior to the first dose of perampanel.

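### The Extension SAP replaces all four Extension A laboratory and vital-sign summaries planned in Protocol Appendix 2 with listings, and section 7 does not name what was dropped

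*SAP*

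**What the plan says.** Protocol Appendix 2 sets out the Extension A safety analyses over the whole time on perampanel. For laboratory data it plans descriptive statistics of values and changes from baseline, low/normal/high shift tables, and an incidence of markedly abnormal values ("Clinical laboratory results post-baseline will be evaluated for markedly abnormal values"). For vital signs it plans descriptive statistics of values and changes from baseline.

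The Extension SAP says in section 5.5: "Clinical laboratory parameters and vital signs data will be listed". Section 5.5.3 repeats "Laboratory results will be listed" and section 5.5.4 "Vital signs data will be listed". Section 8.2.1 nevertheless keeps a rule that such tables would need: "The baseline value for all safety endpoints will be the last non-missing measurement occurring prior to the first dose of perampanel". Section 5.1.2 still carries secondary endpoint 8: "Incidence of AEs and SAEs, changes in clinical laboratory values, and vital signs". Section 7 attributes limited summaries to early termination and identifies no output.

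**The concern.** Protocol 9.1.3 gives long-term safety as one purpose of the 52 weeks of Extension A. That phase holds the perampanel data beyond the 18-week Core, at doses above 8 mg/day (up to 12 mg/day outside Japan), and in subjects who switched from placebo. The Revision History for version 4.0 ties the fasting glucose and lipid samples to a signal for weight gain and raised triglycerides. Changes of that kind can build slowly without prompting an adverse event report.

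Under the Extension SAP, a reader judging long-term use would see no count of subjects whose laboratory values became markedly abnormal. There would also be no summary of weight or fasting lipid change. Those values would have to be pieced together from listings.

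**Working it through.** The plan states no figure to reproduce. The check is a comparison of texts, followed by a simple scale.

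**1. Planned against kept**

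| Protocol Appendix 2, Extension A | Extension SAP |
|---|---|
| Laboratory values and change from baseline | Listing (5.5, 5.5.3) |
| Laboratory shift tables | Listing (5.5, 5.5.3) |
| Incidence of markedly abnormal laboratory values | Listing (5.5, 5.5.3) |
| Vital-sign values and change from baseline | Listing (5.5, 5.5.4) |

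Kept as aggregate output: 0 of 4.

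**2. Whether another planned output fills the gap**

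- *Core tables.* Core SAP 5.6.3 and 5.6.4 do summarise laboratory and vital-sign changes, but under Core SAP 8.2.2 the window for these variables "ends 14 days after the last dose of double-blind study medication".
- *Adverse event tables.* Extension SAP 5.5.2 and 5.5.2.1 tabulate TEAEs, SAEs and discontinuations. Under Protocol 9.5.1.5 a laboratory result counts as an adverse event if it leads to intervention or to stopping or withholding drug; an isolated abnormality is otherwise left to judgement. Results with the Hy's Law pattern are always SAEs, so they are tabulated.
- *Extension B.* Protocol Appendix 4 plans laboratory and vital-sign changes by visit, weight included, over Core, Extension A and Extension B time, but only for subjects who enter Extension B. Protocol 9.7.1 foresees a separate SAP for it. The supplied Extension SAP covers Extension B only for disposition (5.1.5) and exposure (5.5.1).

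**3. Scale, in planned perampanel weeks per 1:1 randomised pair**

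Inputs are Core 6 + 12 = 18 weeks and Extension A 6 + 46 = 52 weeks. Let D be the mean Extension A duration, taken as equal in both arms with all subjects rolling over.

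- Total perampanel weeks = 18 + 2D
- Weeks after the Core = 2D
- Weeks after the Core, less the 14-day Core window in each subject = 2D − 4

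| D (weeks) | Share after the Core | Share allowing the 14-day window |
|---|---|---|
| 52 (planned) | 104/122 = 85.2% | 100/122 = 82.0% |
| 26 (assumed) | 52/70 = 74.3% | 48/70 = 68.6% |
| 13 (assumed) | 26/44 = 59.1% | 22/44 = 50.0% |

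The share rises with D, so 85% is the ceiling for the planned schedule. The last column is generous to the plan, because a placebo switcher's first two weeks on perampanel would appear in the Core tables under placebo. The values D = 26 and D = 13 are illustrative; the documents do not give actual duration.

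**4. What the fasting samples allow**

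Protocol Table 8 schedules Extension A on-treatment laboratory tests at Visits 8, 10, 12 and 14, and marks only Visit 14 and Early DC as fasting. In the Core, Protocol Table 5 marks Visits 2 and 7 as fasting. The planned fasting interval is therefore 491 − 1 = 490 days for subjects randomised to perampanel and 491 − 127 = 364 days for placebo switchers. Protocol Appendix 1 defines high glucose Grades 1 and 2 on fasting values, so grading Visits 8, 10 and 12 without distinction would misclassify glucose. The same caution applies to triglycerides (Grade 2 begins above 300 mg/dL).

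**The case against.** The strongest defence is that the reduction is disclosed and has a reason. Section 7 is the place for such a statement, early termination is a legitimate ground, and Protocol 9.7.5 lets the sponsor revise the SAP and describe the change in the study report. This stands against any inference of a concealed deviation, which the documents do not support. It does not explain why nothing in aggregate remains for these data when the same SAP keeps 13-week efficacy summaries (5.3.1), SMQ groupings (5.5.2.1) and a C-SSRS table (5.5.6.1).

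A reader might also infer that the SAP breaks its own commitment by keeping endpoint 8. That is weak evidence. Extension SAP 5.1 repeats the Core endpoint list almost word for word, including items it plainly does not analyse, such as the double-blind primary endpoint and the modelled steady-state concentration. The scope sentence in section 5 is likewise qualified as general. The departure from Appendix 2 carries the point.

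Nor do the documents support saying that no aggregate table exists anywhere beyond the Core. Appendix 4 plans them for Extension B entrants, and whether they were produced cannot be determined here.

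Finally, all values are listed, and the adverse event definition in Protocol 9.5.1.5 is broad enough to include abnormal laboratory findings. The gap is therefore confined to changes that were not reported as events. The data are also uncontrolled, which limits what any table could show.

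**Conclusion.** The point holds in a limited form. None of the four Appendix 2 laboratory and vital-sign outputs survives in the supplied Extension SAP, and section 7 does not say which were dropped. For the full Extension A population, changes that never become adverse events have no aggregate table in the supplied SAPs.

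The 85% share should not be read as the proportion of actual exposure affected. It assumes full roll-over and completion in a study that ended early; the assumed shorter durations give 50% to 74%. Person-weeks are only a rough scale, since laboratory tests fall at four scheduled on-treatment visits. This is a gap in long-term safety reporting that can be closed cheaply. It does not affect the Core efficacy conclusions.

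**What to change.** Amend Extension SAP 5.5, 5.5.3 and 5.5.4 to add two overall tables (not by visit) on the Safety Analysis Set (Extension), overall and by the age groups in section 5.2.4.

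1. **Markedly abnormal laboratory values.** Number (%) of subjects with a treatment-emergent markedly abnormal value, using the rule in Protocol 9.7.1.8: a rise from the pre-perampanel baseline to Grade 2 or higher, or Grade 3 or higher for phosphate. Grade glucose and triglycerides on fasting samples only, or show fasting and non-fasting results separately.
2. **Change to last on-perampanel value.** Weight, and fasting triglycerides, cholesterol and glucose, with n in each row. The fasting baseline is Visit 2, or Visit 7 for placebo switchers; the endpoint is Visit 14 or Early DC. Footnote that weight change in subjects under 18 includes growth. Appendix 2 does not name weight in its vital-sign analysis paragraph, but Protocol Table 8 collects it with the vital signs.

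In section 7, name the Appendix 2 outputs that remain as listings: shift tables, blood pressure, pulse and the other laboratory changes. Naming them without adding the tables would settle the disclosure but leave the long-term summary missing.

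The cost is modest programming on data already collected, with the baseline and grading rules already defined. The tables would describe change without attributing it to perampanel, and the number with a late fasting sample is unknown and may be small.

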5.5.5 Electrocardiograms

ECG was not obtained during the extension.

5.5.6 Other Safety Analyses

5.5.6.1 C-SSRS

The following summary will be presented for the treatment duration (defined as the period from the date of first dose up to 28 days after the date of last dose, inclusive) .

Number (percentage) of subjects with any treatment-emergent report of suicidal behavior, suicidal ideation, and suicidality (suicidal behavior and/or ideation) will be displayed. A treatment-emergent report of suicidal behavior, suicidal ideation, or suicidality is an answer of 'Yes' to any question in the respective category during the treatment duration.

5.6 OTHER ANALYSES

Not applicable.

5.6.1

CCI

CCI

5.7 EXPLORATORY ANALYSES

There will be no exploratory analysis.

6 INTERIM ANALYSES

No interim analyses are planned for this study.

7 CHANGES IN THE PLANNED ANALYSES

Limited data summaries are being produced due to the early termination of the study. Any future changes to the analysis will be documented separately and will be addressed in the Clinical Study Report.

8 DEFINITIONS AND CONVENTIONS FOR DATA HANDLING

8.1 EFFICACY DATA HANDLING

8.1.1 Baseline Seizure Frequency

For the summaries of overall perampanel treatment duration, all diary data before the first perampanel dose date will be used in the computation of the baseline seizure frequency per 28 days. For subjects assigned to perampanel treatment during the Core Study, baseline will be computed from the Prerandomization Phase of the Core study. For subjects assigned to placebo treatment during the Core Study, baseline would be computed from data during the Core Study plus the Prerandomization Phase of the Core Study.

8.1.2 Treatment Duration for Efficacy Analyses.

The treatment duration for diary seizure data are defined as follows:

- The date of first perampanel dose during the Core Study to the last perampanel dose during the Extension Phase A for subjects assigned to perampanel treatment during the Core Study.
- The date of first to last perampanel dose during Extension Phase A for subjects assigned to placebo treatment during the Core Study.

8.1.3 Seizure Frequency Formulae

The following formula will be used to estimate the “seizure frequency per 28 days” period for each subject, where “Y” is the number of days with valid diary data for that period:

Seizure frequency = Number of seizures of type(s) of interest (captured over Y days) x 28/Y days.

8.2 SAFETY DATA HANDLING

8.2.1 Baseline safety

The baseline value for all safety endpoints will be the last non-missing measurement occurring prior to the first dose of perampanel.

8.2.2 Treatment Duration for Safety Analyses

For AEs, the perampanel treatment duration is considered to begin:

- at the first dose of perampanel in the Core Study and ends 28 days after the last dose of perampanel in Extension Phase A for subjects assigned to perampanel treatment during the Core Study
- at the date of first perampanel dose to 28 days after the last dose of perampanel in Extension Phase A for subjects assigned to placebo treatment during the Core Study.

The Post-treatment duration will begin on the day after the permpanel treatment duration during Extension Phase A.

AEs for the subject were collected and reported on the CRF starting from the time subject signed informed consent to the last visit in the Treatment Phase following subject's last dose. Serious AEs were collected for 28 days after the last dose.

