Safety analyses will be performed similarly to the Core Study analyses and all analyses will be on the perampanel treatment duration (Randomization Phase + Extension A + Extension B for subjects randomized to perampanel and Extension A + Extension B for subjects randomized to placebo). TEAEs are defined as AEs occurring from the time of first perampanel through 28 days after the last perampanel dose. Baseline for laboratory and vital sign parameters is the last non-missing value before first perampanel dose.

Interim Analyses

Not applicable

Sample Size Rationale

Seventy-one (71) subjects will be randomized to each treatment arm and this sample size will provide adequate power for the primary endpoint and the key secondary endpoints.

Primary endpoint percent change from baseline in drop seizures:

Placebo rates in drop seizures in the rufinamide and clobazam clinical trials were +1.4%, and -12.1%, respectively. In the active treatment arm, rufinamide had a median decrease of 42.5% in drop seizures and clobazam had mean decreases of 41.2%, 49.4%, and 68.3% for the low, medium, and high doses, respectively. A standard deviation of ~63% was observed for both rufinamide and for the medium dose of clobazam for drop seizures. It is assumed that comparable results will be seen in this trial for the placebo and perampanel treatment arms for drop seizures.

A sample size of 71 subjects in each treatment arm in the FAS will have 94% power to detect a treatment difference in median percentage seizure frequency change in drop seizures per 28 days of 40% (common SD of 63%) between placebo and perampanel based on a Wilcoxon rank-sum test at the 0.05 two-sided significance level.

50% responder rate for drop seizures:

A sample size of 71 subjects per treatment arm will have 97% power to detect a 30% difference in responder rate proportions between placebo (assuming a placebo response rate of 20%) and perampanel treatment groups at the 0.05 two-sided significance level in drop seizures per 28 days using a two-group chi-square test.

Percent change in seizure frequency for total seizures:

Decreases in total seizures for placebo, and low, medium, and high doses in the clobazam trial were approximately 9%, 35%, 45%, and 65% respectively; common standard deviations ranged from 63% to 83%. It is assumed that comparable results will be seen in this trial for the placebo and perampanel treatment arms for total seizures.

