The sponsor reserves the right to terminate the program at any time.

Study Drug Supplies

Perampanel will be supplied as 2-mg oral tablets and 0.5 mg/mL oral suspension. It is recommended that oral tablet be used for dosing subjects ≥ 12 years of age, and oral suspension for subjects < 12 years of age. However, the most appropriate formulation may be selected based on the subject's condition and at the discretion of the investigator. The same formulation used in the Core Study and Extension A for a given subject should be used throughout the course of the study, including Extension B, unless a change in formulation is medically indicated.

Schedule of Procedures/Assessments

Table 10 presents the Schedule of Procedures/Assessments for the Extension B. During Extension B, laboratory tests will be performed by the local laboratory.

Assessments

Safety Assessments

Safety will be assessed by monitoring of AEs, withdrawal from treatment, clinical laboratory tests, vital signs, and weight.

Other Assessments

Concomitant medication usage will be monitored.

Statistical Analyses

Analysis Sets

The Safety Analysis Set (Extension B) is the group of subjects who received at least one dose of study drug and had at least one postdose safety assessment in Extension B.

Safety Analyses

All safety analyses will be performed on the Safety Analysis Set. Safety data that will be evaluated include TEAEs, and vital signs.

Safety analyses will be performed similarly to the Core Study analyses and all analyses will be on the perampanel treatment duration (Randomization Phase + Extension A + Extension B for subjects randomized to perampanel and Extension A + Extension B for subjects randomized to placebo). TEAEs are defined as AEs occurring from the time of first perampanel through 28 days after the last perampanel dose. Baseline for laboratory and vital sign parameters will be the last non-missing value before first perampanel dose.

Adverse Events

The AE verbatim descriptions (investigator terms from the CRF) will be classified into standardized medical terminology using MedDRA. Adverse events will be coded to the

MedDRA (version 18.1 or higher) lower level term closest to the verbatim term. The linked MedDRA PT and primary SOC are also captured in the database.

A TEAE is defined as an AE that emerges during treatment, having been absent at pretreatment (Baseline) or

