5.5.1 Extent of Exposure

Total perampanel exposure will be calculated as the number of days between the date the subject received the first dose of perampanel (from Core Study or Extension Phase) and the date the subject received the last dose of study drug in Extension Phase (A or B).

The mean, modal, median, maximum and last daily dose over the conversion, extension maintenance (A+B), overall extension and overall perampanel treatment duration will be summarized.. The mean daily dose will be calculated by taking the average of all the doses taken weighted by the total duration of exposure and rounded to 1 decimal place.

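### The Extension SAP counts perampanel exposure through Extension B but closes the adverse-event window 28 days after the last Extension A dose, so the two periods do not match

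*SAP*

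**What the plan says.** **Exposure and disposition (Extension SAP 5.5.1, 5.1.5).** Total perampanel exposure runs from the first perampanel dose to "the date the subject received the last dose of study drug in Extension Phase (A or B"). Dose is summarized over conversion, "extension maintenance (A+B), overall extension and overall perampanel treatment duration will be summarized". Disposition covers both extensions.

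**Adverse events (Extension SAP 8.2.2).** For subjects randomized to perampanel, the AE treatment duration starts at the first core dose and "ends 28 days after the last dose of perampanel in Extension Phase A". For subjects randomized to placebo it runs "at the date of first perampanel dose to 28 days after the last dose of perampanel in Extension Phase A for subjects assigned to placebo". The section adds: "The Post-treatment duration will begin on the day after the permpanel treatment duration during Extension Phase A".

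**What reaches the tables (Extension SAP 5.5.2, 5.5.2.1).** Only treatment-emergent AEs are tabulated. All AEs are listed.

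**Protocol, Extension B.** The Synopsis (Safety Analyses, Extension B) states that "all analyses will be on the perampanel treatment duration (Randomization Phase + Extension A + Extension B for subjects randomized to perampanel"); in the placebo arm the period is both extensions. Appendix 4 repeats this and adds: "TEAEs are defined as AEs occurring from the time of first perampanel through 28 days after the last perampanel dose".

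**Protocol, Extension A, and SAP scope.** The Synopsis and Appendix 2 limit the Extension A safety period to the Randomization Phase plus Extension A (Extension A alone for core-placebo subjects). Extension SAP section 5 sets the general scope of endpoints and analyses as Core and Extension A. Protocol 9.7.1 promises separate SAPs for Extensions A and B.

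**The concern.** From the 29th day after the last Extension A dose, the same day on drug counts as exposure under 5.5.1 and as post-treatment under 8.2.2. A new event on that day is not treatment-emergent under 8.2.2, so it misses the TEAE, treatment-related, serious AE, discontinuation and SMQ summaries. The day itself still lengthens the exposure reported in the same set of tables. Extension SAP section 7 attributes the limited summaries to early termination but does not declare this difference.

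Secondary objective 7 covers safety during the Extension Phase, and Extension B holds the longest exposures. A reader who sets the incidence tables beside the exposure table would take the events to have been counted over all the exposure shown. Events of late onset are the ones that would be missing.

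**Working it through.** The plan states no figure to reproduce. The check compares two windows and then sizes the gap under assumed stays.

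**Step 1. Does 8.2.2 govern the tables?** The TEAE definition in Extension SAP 5.5.2 refers to events during treatment and gives no end date. The missing-date rule in 5.2.5 ties treatment emergence to the perampanel treatment duration. Section 8.2.2 is the only place where that duration is given an end for AEs, so read together these rules exclude the later Extension B events from the tables.

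**Step 2. Do the windows differ within this SAP?**
- Exposure and dose: to the last dose in A or B (5.5.1).
- AEs: to 28 days after the last dose in A (8.2.2).
- C-SSRS: to 28 days after the last dose, with no extension named (5.5.6.1).

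**Step 3. Share of Extension B on-drug days outside the AE window.** Inputs: 28 days (8.2.2); a stay of D days in Extension B (assumed, since Appendix 4 sets no fixed length and schedules visits every 12 weeks). Extension B is taken to start at the last Extension A dose with no gap. This fits Table 10, where the final Extension A visit supplies the Extension B Day 1 assessments.

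Share outside = (D − 28)/D for D of at least 28:
- 8 weeks: (56 − 28)/56 = 50%
- 12 weeks: (84 − 28)/84 = 67%
- 24 weeks: (168 − 28)/168 = 83%
- 52 weeks: (364 − 28)/364 = 92%

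**Step 4. Share of all counted exposure that the AE window covers.** Base for an Extension A completer: 52 weeks = 364 days if randomized to placebo; 18 core weeks + 52 weeks = 126 + 364 = 490 days if randomized to perampanel. Coverage = (base + 28)/(base + D).

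| Weeks in B | Core placebo | Core perampanel |
|---|---|---|
| 12 | 392/448 = 87.5% | 518/574 = 90.2% |
| 24 | 392/532 = 73.7% | 518/658 = 78.7% |
| 52 | 392/728 = 53.8% | 518/854 = 60.7% |

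**Step 5. After the change.** If the AE window ended 28 days after the last perampanel dose in A or B, no Extension B on-drug day would fall outside it.

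**The case against.** The best defence is that 8.2.2 is the consistent section and 5.5.1 the stray one. The SAP's general scope is Core and Extension A, its efficacy windows keep to that scope, and the protocol's own Extension A safety period is the Randomization Phase plus Extension A. On this view Extension B AEs belong to the separate SAP that protocol 9.7.1 promises. This stands in part: it makes cutting exposure back to Extension A as legitimate a repair as extending the AE window. It does not remove the mismatch. The scope sentence is qualified as general, 5.5.1 and 5.1.5 expressly include B, and this SAP, which introduces itself as the plan for the extension study, does not defer Extension B AEs elsewhere. No Extension B SAP is among the documents, so whether those events are summarized in another plan is open.

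The defence also limits the harm, and these points stand. This SAP plans subject incidences, with no exposure-adjusted rates and no P-values, so no calculated rate is distorted. Deaths are listed, as is every AE. A subject counts once per preferred term, so a repeat in Extension B of an event already counted would not change an incidence. The derivations sit in programming specifications that are not available here.

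A reader might infer that most Extension B AEs, or nearly all AEs of the longest-exposed subjects, are lost. The documents do not support either. The first needs stays longer than 8 weeks and a constant event rate, neither of which is documented, and early termination may have shortened stays. The second overlooks that these subjects' on-perampanel AEs are counted through Extension A plus 28 days.

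**Conclusion.** The concern holds as an internal inconsistency in the Extension SAP and as a departure from the protocol's Extension B safety period. As 8.2.2 is written, AEs that start on drug more than 28 days after the last Extension A dose are classed as post-treatment and left out of this SAP's summary tables, while the exposure is counted. The effect is confined to the summary tables.

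Its size cannot be stated, because the number of subjects entering Extension B and their time there are not given. The range of 67% to 92% of Extension B on-drug days rests on assumed stays of 12 to 52 weeks and no gap between extensions. Measured against all counted exposure, the AE window still covers about 74% to 79% for an Extension A completer with 24 weeks in B. These are shares of time; they become shares of events only if the AE rate is constant. Severity: should be fixed.

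**What to change.** Make the two windows match, in one of two ways.

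1. In Extension SAP 8.2.2, end the AE treatment duration 28 days after the last perampanel dose in Extension A or B, for both randomized arms, and start the post-treatment period the day after. This follows the protocol's Extension B plan.
2. Or cut the exposure and dose summaries in 5.5.1 at the last Extension A dose, and name the plan that summarizes Extension B AEs over the full perampanel period that the protocol sets for each arm.

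Under either option, record the choice in section 7. The first option costs two sentences of SAP text and a change to one date variable. It needs no new data, since Table 10 of the protocol already collects AEs at every Extension B visit. The second option is also a wording and date change here, but it depends on an Extension B plan being in place.
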